**Elotuzumab and Lenalidomide Dexamethasone Combination (Cycles 3-8)**

Agent	Premedication and Precautions	Schedule	Dose	Route	Cycle Length
Elotuzumab	Premedications are described below	Days 1 and 15	10 mg/kg	Intravenous- See appendix B for more details	
Lenalidomide	None	Days 1-21 of each cycle	25 mg	Oral	28 days (4 weeks)
Dexamethasone	Take with food; recommended to be taken in the morning	Days 1, 15	8 mg	IV	
			32 mg	Oral	
		Day 8	40mg	Oral	

**Elotuzumab and Lenalidomide Maintenance Therapy (Cycles 9-24)**

Agent	Premedication and Precautions	Schedule	Dose	Route	Cycle Length
Elotuzumab	Premedications are described below	Days 1 of each cycle	20 mg/kg	Intravenous-See appendix B for more details	
Lenalidomide	None	Days 1-21 of each cycle	15 mg	Oral	28 days (4 weeks)
Dexamethasone*	Take with food; recommended to be taken in the morning	Day 1 of each cycle	8 mg	IV	
			28 mg	Oral	

\* After discussion with the overall PI, high-dose dexamethasone may be re-added during maintenance due to biochemical progression (progressive increase in SPEP [25% and an absolute increase of 0.5g/d] or UPEP [25% and an absolute increase of 200mg/24hours] on 2 successive evaluations as determined by the IMWG response criteria or documented progression by the FreeLite™ progressive disease criteria in the absence of serum or urine involvement). Dexamethasone should be given as follows after overall PI approval:

Day	Dose	Route
1	8 mg	IV
	32 mg	Oral
8	40 mg	Oral
15	40 mg	Oral

CONFIDENTIAL

This document is confidential. Do not disclose or use except as authorized.

## 5.2 Pre-Treatment Criteria

There are no pretreatment criteria for elotuzumab dosing. Refer to section 6.2 for Lenalidomide pretreatment criteria and 6.3 for Dexamethasone pre treatment criteria.

### 5.2.1 Premedication Regimen in Subjects without a Prior Infusion Reaction

- Premedication is required prior to all Elotuzumab infusions. Refer to table 3 for the guidelines for premedication.

### 5.2.2 Premedication Regimen in Subjects With a Prior Infusion Reaction

To be re-treated with elotuzumab, subjects with a prior infusion reaction must receive H1, H2 blockers and acetaminophen at maximum doses specified (e.g., 50 mg diphenhydramine, 50 mg ranitidine [or equivalent], and 1000 mg acetaminophen) 90-45 minutes before initiating the elotuzumab.

Doses of intravenous dexamethasone above 10 mg require a decrease in the oral dexamethasone. Recommended dexamethasone dosing is summarized below and in Table 3.

For subjects with prior Grade 2 infusion reaction, administer 10 mg IV dexamethasone (instead of 8 mg IV) as the premedication steroid 90-45 minutes before elotuzumab. Subjects should take 30 mg oral dexamethasone 24-3 hours before elotuzumab administration.

For subjects with Grade 3 or recurrent Grade 2 elotuzumab infusion reactions, consultation with the Principal Investigator is recommended. Administer 18 mg IV dexamethasone as the premedication steroid at least 45 minutes before elotuzumab. These patients should receive 8mg of oral dexamethasone 24-12 hours the day prior to elotuzumab administration. Then, administer 14 mg oral dexamethasone at most 3 hours prior to elotuzumab administration.

If a subject with a prior Grade 2 (recurrent) or 3 infusion reaction also requires dose reduction of oral dexamethasone, the dexamethasone dose on the days of elotuzumab infusion should be no less than 18 mg IV (on the day of elotuzumab infusion at least 45 minutes before elotuzumab).

Subjects with a Grade 4 infusion reaction are not eligible to receive additional elotuzumab. These subjects may continue to receive lenalidomide and dexamethasone. Subjects who experience an infusion reaction of any grade should be administered the recommended premedication for that reaction severity for the duration of the trial.

Subjects with prior infusion reactions may receive more aggressive pre-medications after discussion with the Overall Principal Investigator

CONFIDENTIAL

This document is confidential. Do not disclose or use except as authorized.

**Table 3: Recommended Corticosteroid Premedication**

None or Grade 1 Prior Infusion Reaction	24-3 hours prior to Elotuzumab Infusion	32 mg PO Dexamethasone
	90-45 min prior to Elotuzumab Infusion	8mg IV Dexamethasone Diphenhydramine 25-50 mg IV or PO or equivalent H1 blocker Ranitidine 50mg IV or equivalent H2 blocker Acetaminophen 650-1000mg PO
Prior Grade 2 Infusion Reaction	24-3 hours prior to Elotuzumab Infusion	30mg PO Dexamethasone
	90-45 min prior to Elotuzumab	10mg IV Dexamethasone Diphenhydramine 50 mg IV or PO or equivalent H1 blocker Ranitidine 50mg IV or equivalent H2 blocker Acetaminophen 1000mg PO
Prior Grade 3 Infusion Reaction or recurrent Grade 2	24-12 hours prior to Elotuzumab Infusion	8mg PO Dexamethasone
	No more than 3 hours prior to Elotuzumab Infusion	14mg PO Dexamethasone
	90-45min prior to Elotuzumab	18mg IV Dexamethasone Diphenhydramine 50 mg IV or PO or equivalent H1 blocker Ranitidine 50mg IV or equivalent H2 blocker Acetaminophen 1000mg PO

### 5.3 Agent Administration

The order in which elotuzumab and lenalidomide are administered does not matter.

#### 5.3.1 Elotuzumab

Elotuzumab will be administered intravenously at a dose of 10 mg/kg on Days 1, 8, 15 and 22 for the first 2 cycles (a cycle =28 days). During cycles 3 through 8, elotuzumab will be given on days 1 and 15. Elotuzumab will be administered intravenously at a dose of 20 mg/kg only on Day 1 for cycles 9-24. The patient should be observed for 60 minutes after the infusion is complete for cycle 1 and should be observed for 30 minutes after the infusion for subsequent cycles. All patients should have their vital signs checked before and after elotuzumab infusion or per institutional standard. If an infusion reaction occurs, reference section 6.4.2 for guidelines on additional vital monitoring.

Cycle 1 and Cycle 2 treatment may be administered +/- 3 days. For subsequent cycles +/- 7 days is allowed.

CONFIDENTIAL

This document is confidential. Do not disclose or use except as authorized.

### 5.3.1.1 Guidelines for Elotuzumab infusion in subjects with infusion reactions

Please refer to section 6.4 of the protocol.

### 5.3.1.2 Dose Delay or Interruption

Please refer to section 6.4.3 of the protocol.

## 5.3.2 Lenalidomide

Lenalidomide will be given as a single daily oral dose of 25 mg per day on days 1-21 followed by a 7-day rest period for cycles 1-8 and 15 mg per day on days 1-21 for cycles 9-24. Cycle 1 and Cycle 2 treatment may be administered +/- 3 days. For subsequent cycles +/- 7 days is allowed. Dose modification guidelines are described in Section 6.2 (Dose Modifications/Delays).

Lenalidomide capsules should be swallowed whole, and should not be broken, chewed or opened. Administration of lenalidomide should be at approximately the same time each day. Drug may be taken with or without food. If a dose is missed and less than 12 hours has elapsed since the missed dose, the patient can take the dose for that day. If more than 12 hours has elapsed since missing a dose at the normal time, the patient should not take the dose, but take the next dose at the normal time on the following day. If a dose is missed, it should be taken as soon as possible on the same day. If a dose is vomited, the dose should not be made up and the participant should continue with the regular schedule of the drug at the next dose. A drug diary will be provided to participants to record oral administration of doses.

Participants who take more than the prescribed dose of lenalidomide should be instructed to seek emergency medical care if needed and contact study staff immediately. Participants experiencing adverse events may need study treatment modifications (see Section 6.2).

Lenalidomide related resources will be provided to all patients prior to receiving lenalidomide therapy as part of the Revlimid REMS program. For more information regarding program registration and drug ordering, refer to section 8.2.

### 5.3.2.1 Dose Delay or Interruption

Dose modification and delay guidelines are described in Section 6.2 (Dose Modifications/Delays)

## 5.3.3 Dexamethasone

Dexamethasone will be obtained by commercial supply in this study. This may lead to added costs for the participant or the participant's insurance company. It will be given as an oral dose. Dexamethasone should be taken at approximately the same time each day. Doses of oral dexamethasone should be taken with food and administered per the recommended guidelines in Table 3. It is recommended that dexamethasone be taken in the morning to reduce insomnia. A drug diary will be provided to participants to record oral administration of doses.

CONFIDENTIAL

This document is confidential. Do not disclose or use except as authorized.

Please refer to Section 5.1 for instructions on dexamethasone dosing.

#### 5.3.3.1 Dose Delay or Interruption

Dose modification and delay guidelines are described in Section 6.3 (Dose Modifications/Delays).

### 5.4 General Concomitant Medication and Supportive Care Guidelines

#### 5.4.1 Medications permitted at Investigator's Discretion

- Steroids, diphenhydramine, or hydroxyzine, acetaminophen/ paracetamol, H2 inhibitors (e.g., cimetidine), leukotriene inhibitors (montelukast sodium) for the management of elotuzumab infusion reactions. Additional supportive measures should be provided as indicated including oxygen inhalation, epinephrine, and bronchodilators.
- At the discretion of the treating investigator, patients will receive Pneumocystis jiroveci pneumonia (PJP) prophylaxis during treatment (Bactrim or acceptable alternative). This may be discontinued at the start of maintenance therapy, or at the investigator's discretion.
- Stem cell mobilization will be allowed at the time of best response or at the end of 8 cycles for patients who are eligible for stem cell transplant. Stem cell collection may be done sooner after discussion with overall PI. Standard mobilization treatment (with GCSF or with cyclophosphamide or plerixafor, etc) will be used based on Institutional guidelines. Patients may delay treatment for up to 3 weeks after stem cell collection is complete.
- Use of white cell growth factors [G-CSF (Filgrastim or acceptable equivalent)] is allowed for management of treatment induced neutropenia at physician discretion. Daily use of Filgrastim is not allowed, and participants may receive a maximum of 3 doses per week. Filgrastim should be given according to the ASCO guidelines. Pegfilgrastim is not to be used in replace of filgrastim.
- Patients will receive bisphosphonates per recommendations of myeloma therapy. A note should be placed about patients who are not receiving bisphosphonates for clinical reasons such as osteonecrosis of the jaw.
- Nausea/Vomiting: If nausea and/or vomiting is noted at any point in time, premedication with prochlorperazine or other antiemetics may be used before future doses. If nausea persists in spite of the use of standard antiemetics additional symptom management should be as per standard antiemetic guidelines.
- Thromboprophylaxis is required for all participants. Participants may receive

CONFIDENTIAL

This document is confidential. Do not disclose or use except as authorized.

daily aspirin administration (81 or 325 mg), daily enoxaparin (40 mgs), or low molecular weight heparin (type Innohep® 4500 UI anti-Xa as needed) or equivalent to decrease the risk of thromboembolic complications. Aspirin prophylaxis will be the preferred first choice unless contraindicated. It is recommended that if the platelet count falls below 50,000/mm^3, thromboprophylaxis be held to minimize the risk of bleeding and then resumed when platelet counts are equal to or above this level.

- **For patients at high risk for thromboembolic events, full anticoagulation is recommended.**

## 5.5 Criteria for Taking a Participant Off Protocol Therapy

In the absence of treatment delays due to adverse event(s), treatment may continue for *24 cycles* or until one of the following criteria applies:

- Disease progression
  - *Participants who have developed symptoms similar to CRAB criteria or MDE (see section 2.4), but are not attributable to active, symptomatic myeloma may remain on study after discussion with the Overall PI.*
- Intercurrent illness that prevents further administration of treatment
- Unacceptable adverse event(s)
- Participant demonstrates an inability or unwillingness to comply with the oral medication regimen and/or documentation requirements
- Participant decides to withdraw from the protocol therapy
- General or specific changes in the participant's condition render the participant unacceptable for further treatment in the judgment of the treating investigator

Participants will be removed from the protocol therapy when any of these criteria apply. The reason for removal from protocol therapy, and the date the participant was removed, must be documented in the case report form (CRF). Alternative care options will be discussed with the participant.

A QACT Treatment Ended/Off Study Form will be filled out when a participant is removed from protocol therapy. This form can be found on the QACT website or obtained from the QACT registration staff. External sites should submit the form to the Research Project Manager.

In the event of unusual or life-threatening complications, treating investigators must immediately notify the Overall PI, [name] at [contact].

CONFIDENTIAL

This document is confidential. Do not disclose or use except as authorized.

## 5.6 Duration of Follow Up

Participants will be followed for up to **3 years** after removal from protocol therapy or until progression to active symptomatic MM, whichever occurs first. Assessments will be performed every 3 to 6 months ( +/- 28 days ) for up to 3 years. Patients who have undergone stem cell mobilization will also be followed for 3 years after removal from protocol therapy or until progression to active symptomatic myeloma, whichever occurs first. Participants removed from protocol therapy for unacceptable adverse event(s) will be followed until resolution or stabilization of the adverse event.

Participants unable to participate in follow up every 3 months may follow up every 6 months at PI discretion in accordance with standard of care follow-up frequency and COVID precautions. Physical exams and correlative blood draws that are not done due to virtual visits will not be considered violations. Local myeloma labs must be provided to the participating site for data entry purposes. Bone marrow biopsy and scans are strongly recommended yearly after EOT, but not require however, scans and bone marrow biopsy and research samples are required at time of suspected disease progression

The following is required during the Active Follow Up period (for up to 3 years):

1. Physical exams are voluntary during this period
  - a. Virtual visits/telehealth visits are acceptable
2. SPEP and Immunofixation
3. Serum Free Light Chains (SFLC)
4. UPEP and Immunofixation only for those where disease is tracked by the urine
5. Serum Immunoglobulin test
6. PET/CT assessments are strongly recommended yearly and is required at the time of suspected progression
  - a. The same assessment modality should be used consistently across the duration of the trial
7. Bone marrow biopsies are and strongly recommended yearly after EOT and is required at the time of suspected progression
8. Research bone marrow samples will be collected at the time of any bone marrow biopsy/aspirate procedure
9. Research blood will be collected whenever an in person visit to the site occurs. Research blood samples that are not collected at time points in the collection calendar due to COVID precautions or q6 month follow up will not be considered violations unless it is missed at the time of suspected progression.
10. Response
11. CRAB/MDE Assessment
12. Bone marrow biopsy/aspirate results and cytogenetics/FISH if ordered
13. Scan results and modality

CONFIDENTIAL

This document is confidential. Do not disclose or use except as authorized.

Participants who come off active follow up when they pursue other SMM or MM directed therapy will be followed for survival indefinitely which will capture survival stats, and subsequent therapy information.

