## 6. DOSING DELAYS/DOSE MODIFICATIONS

### 6.1 Elotuzumab

No dose reductions for elotuzumab are allowed. If Elotuzumab is held on Day 1 of a new cycle, treatment with Lenalidomide/Dexamethasone will also be delayed. If Elotuzumab is held during any cycle on days 8, 15, or 22, the treating investigator will decide if Lenalidomide will be held using recommended guidance for retreatment below. Dexamethasone should always be given with Elotuzumab. The dose of dexamethasone may be modified per guidance below. Treatment may be delayed for a maximum of 21 days. If a patient must discontinue treatment with lenalidomide, they may continue to receive elotuzumab on study after discussion with the overall principal investigator.

If a patient must discontinue elotuzumab for unacceptable toxicity, they may continue to receive lenalidomide and dexamethasone on study after discussion and approval of the overall principal investigator.

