#### 8.1.7 Administration

Elotuzumab will be given cycle 1 & 2 at 10 mg/kg IV once a week (days, 1, 8, 15, and 22).  
Elotuzumab will be given cycle 3 to 8 at 10mg/kg IV days 1 and 15 every cycle.  
Maintenance elotuzumab will be given at 20 mg/kg IV day 1 every cycle up to cycle 24 (total of 2 years).

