6- Research bone marrow aspirate and biopsy at the same time of clinically indicated bone marrow biopsy and to confirm response.

7- Peripheral blood samples for correlative studies including serum SLAMF7 levels.

8- Oragene kit for germline DNA will be acquired once at any time point from patients enrolled on this study.

9-If C9D1 or confirmation of response BM biopsy was performed within 3 weeks of subsequent time point listed; do not need to repeat BM biopsy.

CONFIDENTIAL

This document is confidential. Do not disclose or use except as authorized.

10- Patients who are not followed for disease response in their urine per IMWG criteria need only bring urine every third cycle and at end of treatment after baseline

11- Follow up will occur approximately every 3 to 6 months (+/- 28days) for up to 3 years after discontinuation of therapy (EOT). Participants unable to participate in follow up every 3 months may follow up every 6 months at PI discretion in accordance with standard of care follow-up frequency and COVID precautions. Physical exams and correlative blood draws that are not done due to virtual visits will not be considered violations. Local myeloma labs must be provided to the participating site for data entry purposes. Bone marrow biopsy and scans are strongly recommended yearly after EOT but are required when there is suspicion of clinical progression. These assessments can be waived due to extenuating circumstances or for insurance coverage reasons. Scans and bone marrow biopsy and research samples are required at time of suspected disease progression if one is performed as part of standard of care procedures.

12- A CD of scans at screening and end of treatment is requested to be sent to the lead site for central review. Screening scans should be sent with the eligibility packet to the lead site

(X)- Indicates this assessment may not be required

**Note:** Research blood and bone marrow studies are voluntary and do not exclude patients from participating

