### **13. STATISTICAL CONSIDERATIONS**

#### **13.1 Study Design/Endpoints**

The primary endpoint of this phase II study is to determine the proportion of high risk

CONFIDENTIAL

This document is confidential. Do not disclose or use except as authorized.

smoldering multiple myeloma (SMM) patients who are progressive free at 2 years after receiving treatment (Elotuzumab + lenalidomide+ Dexamethasone). The secondary objectives include toxicities, objective response rate, time to progression, duration of response, and overall survival. In addition, we will examine the molecular evolution of the tumor cells, the role of circulating tumor cells and immune cells, and the role of NK cells and other immune cells present in the bone marrow in the progression of smoldering MM.

The proportion of patients who achieve progression free at 2 years will be compared to the rate published for the high risk SMM. By the Mayo Clinic model for risk factors, the median time to progression for patients with high risk SMM was only 1.9 years. Therefore, we assume that for this study, a 2-years progression-free rate of 50% will not be considered promising and a true progression free rate of 70% or higher will be considered promising. A single-stage design will be employed with 39 eligible patients entered. If 24 or more of the 39 eligible patients are progression free at 2 years (observed rate of 62%), we will conclude that this treatment warrants further study. The probability of concluding that the treatment is effective if the true rate is 50% is 0.10 and is >0.9 if the true rate is 70%. Assuming an ineligibility rate of 5%, we will accrue 41 patients/per Arm to the trial in order to have 39 eligible patients. A total of 55 patients will be enrolled.

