### 13.1.1 Analysis of Primary Endpoint

Time to progression (TTP) is defined as the time from protocol therapy initiation until documented progression, censored at date last known progression-free for those who have not progressed. At time of final analysis, the 2-year progression-free rate will be estimated using the Kaplan-Meier method with 90% confidence interval per Arm. All patients who have received one dose of study treatment will be included for the TTP analysis, including those who die or are lost to follow-up within 2 years.

The percent of patients who undergo stem cell mobilization and the modality of mobilization will be noted in the study. These patients will not be censored.

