### **13.2 Sample Size, Accrual Rate and Study Duration**

A total of 55 patients will be enrolled. We expect 3.5 years of active accrual (approximately 2 patients per month) and 3 years of follow-up of patients.

The final analyses of progression-based endpoints, such as estimating the 2-year progression-free rate and estimating the TTP distribution, will be conducted at the end of the study, which will occur after either all subjects have progressed or died or 2-years after the initiation of therapy of the last subject enrolled, whichever occurs first.

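### No disease assessment is tied to 24 months from first dose, so progression in the gap after cycle 24 tends to be dated after 2 years and to raise the 2-year progression-free rate modestly

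*Combined protocol and SAP*

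**What the plan says.** - **Endpoint and rule.** Section 13.1 tests the proportion progression free at 2 years. It says that "a 2-years progression-free rate of 50% will not be considered promising", takes 70% as promising, and passes the treatment if 24 or more of 39 eligible patients are progression free.
- **Clock and event.** Section 13.1.1 defines time to progression as "the time from protocol therapy initiation until documented progression, censored at date last known progression-free for those who have not progressed". The 2-year rate is a Kaplan-Meier estimate.
- **Treatment length.** Section 5.1 sets a 28-day cycle and section 5.5 allows 24 cycles. Section 8.1.7 describes maintenance elotuzumab as given "up to cycle 24 (total of 2 years").
- **Reads on treatment.** The section 10 calendar has myeloma labs on Day 1 of every cycle and at End of Tx, with imaging and marrow also at End of Tx.
- **Reads after treatment.** Section 5.6 states "Assessments will be performed every 3 to 6 months ( +/- 28 days ) for up to 3 years", and adds: "Participants unable to participate in follow up every 3 months may follow up every 6 months at PI discretion". Footnote 11 of the calendar gives the anchor: "Follow up will occur approximately every 3 to 6 months (+/- 28days) for up to 3 years after discontinuation of therapy (EOT"). Myeloma labs and a CRAB/MDE assessment are required in this period. Imaging and marrow are recommended yearly and required at suspected progression.
- **Final analysis.** Section 13.2 gives its timing: "which will occur after either all subjects have progressed or died or 2-years after the initiation of therapy of the last subject enrolled". The earlier of the two milestones applies.

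Neither section 5.6, nor the calendar, nor section 13 sets an assessment or window at 24 months from first dose, or says how progression first found after 2 years is to be handled.

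**The concern.** The analysis clock starts at first dose. The follow-up visits are counted from the end of treatment. Twenty-four 28-day cycles are called 2 years but fall about 58 days short, so a patient who completes treatment on schedule is read at about 22 months and, nominally, not again until after 2 years.

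Some progression in this disease is silent. A free light chain ratio crossing the section 11.1 limit, for example, is seen only when the test is done. If it happens after the last on-treatment read and before 2 years, it is documented at the next visit, and the patient is progression free at 2 years in the Kaplan-Meier estimate. The error runs in one direction, towards a higher rate. What is at stake is the go decision, which rests on a single threshold in a small single-arm trial.

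**Working it through.** **1. The plan's own figures.** With X binomial (39, p), P(X ≥ 24) is 0.0998 at p = 0.50 and 0.906 at p = 0.70. Section 13.1 states 0.10 and above 0.9, so its operating characteristics are reproduced.

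**2. Calendar for an undelayed completer.** Days are counted from first dose, with 2 years = 730.5 days.
- End of cycle 24: 24 × 28 = 672 days, or 672 / 30.44 = 22.1 months. Gap to day 730: 730 − 672 = 58 days.
- The documents do not state the exact start of the first follow-up interval, so three starts are shown (3 months = 91 days, 6 months = 182 days, window ± 28 days):

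| Interval counted from | 3-month visit (window) | 6-month visit (window) |
|---|---|---|
| End of cycle 24, day 672 | 763 (735-791) | 854 (826-882) |
| Last lenalidomide dose, 23 × 28 + 21 = day 665 | 756 (728-784) | 847 (819-875) |
| Cycle 24 Day 1, 23 × 28 = day 644 | 735 (707-763) | 826 (798-854) |

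Every nominal date is after day 730. A visit before day 730 is possible only in the early part of the 3-month window, and only on the two earlier starts.

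**3. Illustrated effect on the rate.** Assume a constant hazard and a true 2-year rate of 50%, so S(t) = 0.5^(t/730.5). Then S(672) = 0.5^0.9199 = 0.5285. Let f be the share of patients whose last read before 2 years is at day 672. The recorded rate is q = 0.5 + f × 0.0285.

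| f | q | Extra patients of 39 | P(X ≥ 24) |
|---|---|---|---|
| 0 | 0.500 | 0 | 0.100 |
| 0.25 | 0.507 | 0.3 | 0.116 |
| 0.50 | 0.514 | 0.6 | 0.135 |
| 1 | 0.529 | 1.1 | 0.177 |

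The documents give no value for f.

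**4. Effect of delay.** One 21-day delay moves the end of treatment to day 693. Even with every patient affected, S(693) = 0.518 and the pass probability is 0.146. Three such delays (63 days) exceed the 58-day gap.

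**5. Sensitivity to the benchmark.** Section 13.1 derives its 50% from a median time to progression of 1.9 years. Under the same model that median gives 0.5^(2/1.9) = 0.482 at 2 years, with a pass probability of 0.066. With every patient last read at day 672, the rate is 0.511 and the pass probability 0.126.

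**6. Data cut.** Section 13.2 expects about 2 patients per month. If the cut fell exactly 2 years after the last first dose, and the next visit were at day 756-763, the number of last completers without a read at or after 2 years would be about (756 − 730.5) / 30.44 × 2 = 1.7 to (763 − 730.5) / 30.44 × 2 = 2.1, if all were still progression free.

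**The case against.** **The benchmark may carry the same delay.** The 1.9-year median also rests on documented progression, on a schedule that the documents do not give. If those patients were read at similar intervals, part of the delay is already in the 50%. Step 5 shows too that 50% is rounded up from what the median implies. This stands, and it limits what can be said about a false go. It does not show that the two delays cancel.

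**Few patients may be affected.** An undelayed course is the shortest possible one. Section 6.1 says "Treatment may be delayed for a maximum of 21 days", and delays are also allowed for elective surgery and after stem cell collection. Symptomatic progression can be worked up between visits. This stands as a limit on size. Silent progression is different, because suspicion of it depends on labs that are not scheduled again until after day 730.

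**A reader might infer that the true type I error is 0.177 or higher.** The documents do not support that. The 0.177 needs every patient to be an undelayed completer with no further read before 2 years. Patients who stop early and are seen every 6 months can have larger gaps: spreading last reads evenly over the 182 days before 2 years gives 54.6% and 0.239. But that places all 39 patients on an option reserved for those unable to attend every 3 months. With a quarter of patients in that position, the figure is 0.127. The primary analysis is also a Kaplan-Meier estimate on all treated patients, so pass probabilities for the 24-of-39 count only illustrate it.

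**A reader might infer that the data cut will lose the last patients.** Section 13.2 has the analysis occur after the milestone. The shortfall arises only if the cut is taken on the earliest date, and Kaplan-Meier can carry a few patients censored near day 672.

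**Conclusion.** The gap is real and follows from the plan's own calendar: up to 58 days for an undelayed completer, with the next nominal visit after day 730 on every reading of when follow-up starts. Following the plan as written tends to raise the 2-year progression-free rate. The likely size is modest. Under a constant hazard and a true 50%, it is less than one patient in 39 if half or fewer are affected (pass probability 0.116 at a quarter, 0.135 at half, against 0.100), and about one patient only if all are. Delays and work-up at suspected progression reduce it. Early stoppers on 6-month visits can add to it.

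The documents give neither the number affected nor the assessment schedule behind the benchmark. The direction of the effect on the recorded rate is therefore clear, but the net effect on the chance of a false go cannot be fully quantified. The timing should be corrected because the remedy is cheap and the primary endpoint should not depend on where visits happen to fall.

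**What to change.** - **Section 5.6 and the section 10 calendar.** For every patient still progression free, time the already-required myeloma labs and CRAB/MDE check at 24 months from first dose, with a narrow stated window, for example ± 14 days. A cycle Day 1 or follow-up assessment inside the window counts. Later visits are timed from this one.
- **Section 13.1.1.** State in advance that progression documented at this assessment counts as not progression free at 2 years. Add an interval-censored sensitivity analysis for progression first found later.
- **Section 13.2.** Set the data cut after the close of the last subject's 24-month window.

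The window should stay narrow and centred on 2 years so that the quantity tested still matches the 2-year null. In the model above, reading everyone at the late edge (730 + 14 = day 744) gives a pass probability of 0.087. A wider window that opened at day 702 would give 0.133 at its early edge.

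The cost is amendment wording, one visit moved for completers, one moved or added for some early stoppers, and a slightly later data cut.
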